4.7 Study Flow Chart of Assessments and Evaluations

Measurement	Screening (Month -12 to 0)	Baseline Survey (Month 0)	Baseline CDM Extraction (Month -3 to 0)	Intervention visits (Months 1-12)	CDM Extraction (Months 6, 12, 18)	T2 survey (Month 06)	T3 survey (Month 12)
Informed consent	•						
Demographics	•					•	•
Health literacy level		•					
Randomization		•					
Average daily MED			•		•		
Medical encounters			•		•		
Charlson Comorbidity Index (ICD-9/10)			•		•		
Chronic noncancer pain conditions (ICD-9/10)			•		•		
Mental health diagnoses (ICD-9/10)			•		•		
Alcohol/substance use diagnoses (ICD-9/10)			•		•		
Body mass index (based on height and weight)			•		•		
Health insurance payer			•		•		
Opioid withdrawal medication prescriptions			•		•		
Administer study intervention				•			
EHR template note					•		
Adverse Event Case Report form (as indicated)				•			
Brief Pain Inventory		•				•	•
PROMIS self-report scales: (Pain Interference, Physical functioning, Pain Intensity, Anxiety, Depression)		•				•	•
Current psychotherapy		•				•	•
Self-reported opioid use and intent to taper		•				•	•
Use of intervention content; knowledge check						•	•
Hospitalization or ED visits related to opioid use (overdose or withdrawal) or suicide attempt			•		•	•	•
Death					•		
Adverse Event review and evaluation	•	•	•	•	•	•	•
Fidelity review and evaluation				•		•	•

5. ANALYSIS POPULATIONS

5.1 Intention-to-Treat (ITT)

The primary and secondary analyses will be based on the intention-to-treat (ITT) principle, with data from all participants analyzed according to the arm to which they were randomized irrespective of the amount of intervention received. Participants who are randomized but do not complete the study will be used in all analyses for which data are available. This approach ignores nonadherence, protocol deviations, withdrawal and lost-to-follow-ups. However, in the event a participant is accidentally randomized twice, all data for this participant will be included in the CONSORT diagram; however, the participant's first randomization assignment will only be included in the ITT analyses. The participant's second randomization assignment will be removed from the analysis dataset and subsequent data analyses. Analysis of the ITT population avoids overoptimistic estimates of the efficacy of an intervention resulting from the removal of non-compliers, accepting that protocol deviations occur in actual clinical practice (Heritier, Gebski, & Keech, 2003).

5.2 Per-Protocol Population

As in most pragmatic clinical trials, some participants may not adhere to the intervention they were randomized to receive, reducing fidelity to the intervention as designed and potentially changing the effectiveness of the intervention. The most likely form of nonadherence will be absence from group therapy sessions in the MI+CBT-CP arm or with patients in the SDM arm ceasing interaction with the assigned provider. The potential impact of this nonadherence is underestimating the magnitude of the true treatment effect. To assess this, in addition to the ITT analyses, we will also conduct secondary analyses using a per protocol population consisting of participants that met all inclusion/exclusion criteria, and received a substantial portion of the randomized intervention, defined as at least 4 completed SDM visits and at least 4 completed MI or CBT sessions (out of a total of 1 MI and 8 CBT). Note that the inclusion criterion for baseline MED is based on the most recent prescription, while the baseline value for MED in the analysis is the average MED for the past 90 days. Having a baseline value < 20 is not a protocol violation when the sites indicated that inclusion criterion was met based on the most recent prescription when the patient was assessed. A sensitivity analysis on the per-protocol population will also be conducted by defining this population as those who met all inclusion/exclusion criteria and completed at least 3 SDM visits and at least 3 MI or CBT sessions. This sensitivity analyses are included as many SDM participants may only complete 3 visits with their provider throughout the 12-month intervention phase in the event their opioid prescriptions can be renewed over a 3-month period without an actual clinic visit.

The per-protocol analysis provides a better estimate of the true efficacy of an intervention (i.e., among those who completed the treatment as planned) (Ranganathan, Pramesh, & Aggarwal, 2016). No other analysis populations are defined for this protocol.

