The participant and provider will meet as often as needed for pain management. If the patient and physician decide that an opioid dose change is warranted, the patient may have more frequent visits with the SDM provider. A change in the frequency of visits due to medication changes is part of standard practice for opioid management and will be covered by health insurance. The patient may have a total of 4 to 12 visits over an approximately 12-month period. (We expect about one or more visits every 3 months to assess benefits and harms of opioid therapy. This would be for a patient on a stable dose of opioid medication who will not be adjusting the opioid dose during study follow-up. Patients who undergo opioid tapering may have more frequent follow-up visits to reinforce the provider-patient partnership, discuss potential withdrawal symptoms, such as temporary increase in pain, and assess pain and opioid management based on clinical judgement.)

If participants are assigned to Arm 1 and their provider is trained in SDM, the participant will continue seeing this provider for the 12-month intervention period. If the provider is not trained in SDM, participants will be asked to switch providers for opioid management care, and an SDM-trained provider will be assigned to the participant based on availability. In the study's consent form, participants are told about the potential need to change providers in order to receive opioid treatment from a trained provider. Participants will continue with their current PCP or another provider not trained in SDM for their non-opioid care—such as for acute or chronic conditions—with an understanding that only a provider trained in SDM can manage participants' opioid care.

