#### 8.1.3 Potential Economic Risks

*Cross-reference: UNC IRBIS Application sections A.6.5, A.6.6 (risks), B.5.1 (costs).*

If the participant is randomized to the CBT arm, a co-pay may be required for each CBT session attended.

If the participant is randomized to the SDM arm, and if the participant changes opioid dose, there may be additional visits. These visits are part of the standard of care for opioid management. Clinical sites (Duke, UNC, VUMC) will work with clinic management to tailor delivery of the SDM intervention based on needs of their clinic. For example, one site may choose to enroll only the patients seen by SDM-trained providers whereas another site may have the patient switch all care to an SDM-trained clinician.

Thus, clinics can do one or more of the following if they deliver the intervention as outlined in the protocol:

- Enroll patients from only SDM-trained providers
- Adhere to clinic guidelines that use dual management of pain patients (which is currently in place in some of the clinics)
- Have SDM providers provide primary care as well

We will be fully transparent with the potential respondents when we explain the study to them, that they will be responsible for additional co-pays that may be incurred as part of the research.

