3.1.3 Additional Objectives Not Specifically Listed in the Protocol Objectives section

1. Comparison of intervention groups for other self-reported outcomes of anxiety, pain intensity, depression, Brief Pain Inventory (BPI) pain intensity subscale and pain interference subscale, intent to taper, and discontinuation of opioid use.
2. While multiple subgroup analyses have an inherent risk of inflating Type I error, this trial offers a unique opportunity to generate hypotheses about the profile of patients most likely to benefit from the intervention. Consequently, planned *secondary* analyses will assess potential differential treatment effects (treatment by subgroup interaction) for two subgroups: 1) defined by participants with comorbid mental health conditions and 2) sex.
3. The study will also include descriptive *exploratory* analyses to explore the heterogeneity within each intervention arm separately on opioid reduction (predictors of response) according to covariates of interest including age, baseline pain score, comorbidities (including physical comorbidities and mental health disorders, and past or current alcohol or other substance abuse and related disorders), those taking other medications, patient health literacy level, BMI, and opioid dose used at baseline in 3 categories consistent with CDC guidelines: low (20-49 MED), moderate (50-89 MED), high (90 or more MED); we will also have a category for very low (1-19 Med); and intervention delivery mode (in-person vs telehealth). Testing for heterogeneity of treatment effects for these subgroups will be considered exploratory as opposed to confirmatory, and the results will be interpreted with appropriate caution
4. Determine if there is a threshold for the number of completed SDM visits or CBT sessions that results in a clinically significant decrease in opioid use from baseline, defined as a decrease of 10 MED daily dose.

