9.6.5 Exploratory Evaluation of Heterogeneity of Intervention Response to Opioid Use

We will explore treatment heterogeneity for a set of 10 potential covariates listed below, as specified in the protocol and defined in section 9.2 above:

- presence of substance use disorders (yes/no)
- presence of comorbid diseases (Charlson comorbidity index none vs 1 or more),
- Age (< 50, 50-64, 65+),
- baseline pain (BPI pain severity score of mild, moderate, severe),

- health literacy (high, average, and low),
- BMI categories (obese vs. not obese),
- Taking non-opioid pain medications prescribed (yes/no) per T1 survey
- Baseline opioid dose categories (very low, low, moderate, and high).
- Intervention delivery mode (in-person vs. telehealth),
- Number of intervention visits/sessions received: 0, 1-2, 3-4, >4

Testing for heterogeneity of intervention effects for these subgroups will be considered *exploratory*, and the results will be interpreted with appropriate caution. The outcome of interest for these analyses will be change from baseline to 12-months in average prescribed daily opioid dose (in MED). Analyses for these 10 covariates will be conducted the same as for the 2 specified subgroups above (Section 9.6.4), except that p-values will be interpreted descriptively only.

Each covariate will be added individually to a repeated measures MMRM models similar to the primary model described above while intervention arm is still adjusted for in the model .

9.6.6 Percent of Participants Who Experienced an Increase in Pain and Decrease in Opioid Dose

We will explore the percentage of participants per intervention arm who experienced an increase in pain and a decrease in opioid dose. For this analysis, we will create a binary variable for both the PROMIS Pain Interference and Physical Functioning outcomes that identifies participants that experienced an increase in these measures at 12-months since baseline (i.e.: an increase in the Pain Interference T-Score at 12-months and a decrease in the Physical Functioning T-Score at 12-months). We will then categorize their opioid use at 12-months in comparison to baseline as: unchanged (within +/- 10 MED), decreased (<10 MED), or increased (>10 MED).

We will provide descriptive statistics via contingency table that displays the count and proportion of participants, per intervention arm, that experienced an increase in pain but a decrease in opioid prescriptions. No hypothesis or statistical testing will occur.

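### SDM per-protocol membership rests on a visit count that dose change may itself raise, so the SAP cannot call the per-protocol result the better efficacy estimate

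*SAP*

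**What the plan says.** SAP 5.2 admits participants to the per-protocol population if they met the eligibility criteria and received a substantial part of their assigned intervention, "defined as at least 4 completed SDM visits and at least 4 completed MI or CBT sessions". Read by arm, that is 4 SDM visits in Arm 1 and 4 MI or CBT sessions in Arm 2. Protocol 5.1 gives the same cut-offs. SAP 9.4 repeats the primary model in this population. SAP 5.2 tells the reader how to take the result: "The per-protocol analysis provides a better estimate of the true efficacy of an intervention".

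SAP 5.2 also plans a sensitivity population at 3 visits or sessions. Its reason is that "many SDM participants may only complete 3 visits with their provider throughout the 12-month intervention phase" when prescriptions can be renewed without a clinic visit.

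The protocol describes what drives SDM visit frequency. Section 6.2.1: "If the patient and physician decide that an opioid dose change is warranted, the patient may have more frequent visits with the SDM provider". The same section: "Patients who undergo opioid tapering may have more frequent follow-up visits to reinforce the provider-patient partnership". Section 8.1.3, on the SDM arm: "if the participant changes opioid dose, there may be additional visits".

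Two other places use the same count. Objective 4 in SAP 3.1.3 is to "Determine if there is a threshold for the number of completed SDM visits or CBT sessions that results in a clinically significant decrease" of 10 MED. SAP 9.6.5 lists "Number of intervention visits/sessions received: 0, 1-2, 3-4, >4" among its exploratory covariates, modelled with an arm interaction as in SAP 9.6.4.

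**The concern.** A per-protocol comparison gives up the protection of randomisation. It is informative about efficacy only if the reasons for staying in the set are unrelated to the outcome, or are adjusted for. Here the documents themselves describe a path from outcome to membership. A participant whose dose is being reduced may be seen more often, and those extra visits can carry the participant over the cut-off. A participant on stable renewals may fall short of it.

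The path is documented in one arm only, so it need not cancel in the comparison. At stake is how the trial is read. If ITT is inconclusive and the per-protocol result differs, the SAP directs the reader to trust the per-protocol result. Likewise, a visit threshold reported as producing a 10 MED decrease could be a consequence of that decrease.

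**Working it through.** **1. Can taper visits count toward the threshold?** Protocol 6.2.1 says only an SDM-trained provider may manage an Arm 1 participant's opioid care. SAP 4.4.1 derives SDM visits from attendance with a trained SDM provider, clinic notes and smartphrases. Taper follow-up visits can therefore count.

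**2. Where do stable patients sit?** Protocol 6.2.1 expects about one or more visits every 3 months on a stable dose, so 12 / 3 = about 4 a year, within a 4-to-12 range. SAP 5.2 says many may have 3. Stable patients are at the cut-off or just below it, which is where extra taper visits make most difference.

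**3. Do the windows overlap?** SAP 9.2 counts SDM visits over the whole 12-month intervention phase. SAP 9.3 takes the 12-month outcome as the average over months 9 to 12. The windows are not identical, but a taper at any time in the year can raise the count, and its effect on dose can be present in months 9 to 12.

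**4. Is there a counterpart in Arm 2?** Protocol 6.3.1 describes one MI session and up to 8 CBT sessions, anticipated within about 3 months though possibly longer. No passage ties their number to a dose change.

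**5. Yardstick.** The planned difference is 10 MED with SD 40. For 80% power at two-sided 0.05, the normal formula gives 252 per arm and the t-based solution 252.1, rounded up to 253, or 506 in total as stated. Then 506 × 1.2 = 607.2, stated as 608. Nothing below depends on this except the comparison with 10 MED.

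**6. Illustration of size.** The documents give no taper rate, taper size or visit distribution, so all inputs here are assumptions. Let p be the share of SDM participants who taper, R their dose reduction relative to stable patients, and t and s the probabilities that tapering and stable patients reach 4 visits. Assume no true arm difference and no outcome-related selection in Arm 2.

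- Taper share in the set = p·t / (p·t + (1 − p)·s)
- Shift in SDM mean change = −R × (share − p)

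With p = 0.30 and R = 25 MED:

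| t | s | Taper share | Shift (MED) |
|---|---|---|---|
| 0.90 | 0.30 | 0.27/0.48 = 56% | −6.6 |
| 0.80 | 0.30 | 0.24/0.45 = 53% | −5.8 |
| 0.90 | 0.50 | 0.27/0.62 = 44% | −3.4 |
| 0.80 | 0.50 | 0.24/0.59 = 41% | −2.7 |
| 0.90 | 0.70 | 0.27/0.76 = 36% | −1.4 |
| 0.90 | 0.75 | 0.27/0.795 = 34% | −1.0 |
| 0.90 | 0.90 | 30% | 0 |

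The rows with s at 0.70 to 0.75 follow the protocol's expectation that stable patients usually reach about 4 visits. Those with s at 0.30 to 0.50 follow the SAP's remark that many reach only 3.

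**7. Effect of the 3-visit set.** Take visit counts as Poisson with mean 3 to 4 (stable) and 6 to 8 (tapering), p = 0.30 and R = 30. The spurious SDM advantage is 2.7 to 7.1 MED at the 4-visit cut and 1.4 to 3.7 at the 3-visit cut. Over p = 0.20 to 0.40 and R = 20 to 40, the ranges are 1.4 to 9.8 and 0.7 to 5.3. With mean 4 in both groups the bias is zero at either cut.

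**8. Effect on a nominal test.** With SD 40 and an assumed 100 to 150 per arm in the set, the standard error is 40 × √(2/n). A bias of 3 MED then gives a two-sided false-positive rate of about 8% to 10%. A bias of 6 MED gives about 19% to 26%.

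**The case against.** The other side has several good points.

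- **The text is permissive.** The protocol says visits may increase, and it expects stable patients to reach about 4. A reader might infer that the SDM set is selected on the outcome outright. The documents support only partial dependence.
- **Direction is not settled.** A reader might infer that the comparison is biased toward SDM as a matter of fact. Sections 6.2.1 and 8.1.3 also speak of dose change in general, so increases could add visits and offset some of the lean. In Arm 2, participants who keep attending may be those more motivated to reduce. Protocol 6.3.1 and 6.3.2 link the sessions to opioid goals and planning. That is confounding rather than reverse causation, but it could enrich the MI+CBT set for reducers too, and the illustration sets it to zero.
- **The plan already limits the damage.** The 3-visit set roughly halves the illustrated bias. SAP 9.4 calls the per-protocol analysis supportive, SAP 7.6 treats comparisons outside the primary and two key secondary tests as descriptive, and SAP 5.1 warns against over-optimism from removing non-compliers. SAP 9.6.5 already reads its p-values descriptively.

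All of this stands, and it limits the claim. It does not rescue the sentence in SAP 5.2. The 3-visit set is justified by renewals, not by outcome-dependent selection, and it leaves some bias wherever tapering raises the chance of qualifying. A bias of unknown sign and size is itself a reason not to rank this estimate above ITT.

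**Conclusion.** Wrong as written. The statement that the per-protocol analysis better estimates true efficacy is not supported, because in the SDM arm membership can depend partly on dose change. The causal wording of objective 4 has the same fault, and the sessions-received analysis needs the same caution.

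The likely lean is toward SDM, because the protocol names tapering specifically as a source of visits and documents no matching link in Arm 2. Neither direction nor size can be derived from the documents. The illustrated shift of about -1 to -6.6 MED rests on 30% of SDM participants tapering by 25 MED, the qualifying probabilities in the table, and no selection in Arm 2. It is zero if tapering does not change the chance of qualifying.

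A reader might infer that the trial's main conclusion is compromised. It is not: the ITT primary test does not use the visit count.

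**What to change.** - **SAP 5.2:** delete the sentence "The per-protocol analysis provides a better estimate of the true efficacy of an intervention" together with its parenthetical qualifier. State that both per-protocol sets (4 and 3 visits or sessions) are selected after randomisation on a count that dose change can influence in the SDM arm, and that they are descriptive and support no efficacy claim over ITT.
- **SAP 3.1.3, objective 4:** replace 'results in' with 'is associated with'.
- **SAP 9.6.5:** keep the exploration by sessions received, since protocol 5.3.3 specifies it. Add a within-arm tabulation and the same reverse-causation caveat.

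Two further changes may suggest themselves and should not be made. Baseline covariates in the per-protocol model cannot remove a path that runs from the outcome to the visit count. Dropping the arm interaction for sessions received would conflict with protocol 5.3.3.

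The cost is SAP wording and one table. The downside is that the per-protocol result carries less weight in the report.

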6. SAMPLE SIZE DETERMINATION

Sample size estimates were generated to provide robust power to detect minimal clinically important differences (MCID) in reduction of opioid use between the 2 study arms.

A total sample size of 506 participants (253 per study arm) will provide 80% power to detect an effect size of a difference of 10 MED between the SDM and MI+CBT intervention arm using an analysis of covariance model with $\alpha=0.05$ and assuming a baseline model-adjusted standard deviation for change from baseline of 40 MED. The sample size was inflated by 20% (608 total participants; 304 per study arm) to account for potential variance inflation associated with CBT group delivery (based on a group

size of 8 and an interclass correlation coefficient of 0.01) and a potential loss of follow-up opioid prescription data on as many as 12% of participants.

For the PROMIS secondary outcome measures, the minimally important difference (MID) for the physical function scale is 2 units, whereas the MID for the pain interference scale is 3.5 units. For both instruments, we assume the standard deviation for change from baseline is 10 (see section 9.2 for a more thorough description of these secondary measures). With the planned total of 608 randomized participants and assuming 20% of those have missing PROMIS scale responses, the power for the PROMIS Pain Interference score is 96%, while the power for the PROMIS Physical Functioning scale is 57% (Table 6.1).

Note that the enrollment was slower than planned, and due to timeline constraints was stopped prior to reaching 608 randomized participants. Final study enrollment was 526 randomized participants. As of June 2023 (DSMB report), study discontinuation was at 20%;, but survey completion rate was tracking around 60% (40% missing, higher than the planned levels). Approximate post-hoc power based on the final sample size is provided in Table 6.1.

Table 6.1. Power for Primary and Key Secondary Outcomes

Total sample size	Primary aim: Power for opioid MED ¹	Secondary aim: power for PROMIS Pain Interference ²	Secondary aim: Power for PROMIS Physical Functioning ²
Planned 608	80%	96%	57%
Approximate post hoc power based on randomized (n=526)	75% based on protocol- assumed level of missing opioid prescription data	85% Based on number of completed surveys	40% Based on number of completed surveys

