**Table 8. Power for Primary and Key Secondary Outcomes with N=608 Randomized Participants**

Total sample size	Primary aim: Power for opioid MED*	Secondary aim: power for PROMIS Pain Interference*	Secondary aim: Power for PROMIS Physical Functioning*
608	80%	96%	57%

\*MID, SD, and loss to follow-up rates are the same as noted in Table 7.

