7.6 Multiple Comparisons and Multiplicity

The comparison of the intervention arms for the primary outcome at 12-months is the primary formal hypothesis test (0.05 level of significance, two-tailed). Statistical significance of the 2 key secondary outcomes (PROMIS physical functioning and PROMIS pain interference at 12 months) will be assessed with adjustment for multiple comparisons using the Hochberg modification to the Bonferroni adjustment (discussed further in section 9.5.1). Primary and secondary hypothesis tests resulting in nonsignificant p-values will be interpreted as inconclusive. All other statistical comparisons between intervention arm will be considered descriptive in nature with no adjustment for multiple comparisons, and all confidence intervals will be generated using 95% bounds.

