9.5 Analysis of Secondary Outcomes

9.5.1 PROMIS Pain Interference and Physical Functioning

Secondary analyses will generate point and interval estimates of mean change in the PROMIS physical function and PROMIS pain interference T-scores from baseline to 6 and 12 months between the 2 intervention arms. The 12-month timepoint is primary. These secondary analyses will use appropriate linear mixed model-based approaches analogous to those described for the primary outcome analysis (section 9.3), to take advantage of the data from 6-month assessments for participants who did not complete the 12-month assessment as well as the correlation between the timepoints for participants with both assessments to estimate the change at 12-months for all participants with at least one post-baseline assessment.

Since comparisons at 12 months for these outcomes are two protocol-specified secondary analyses, statistical significance will be assessed with adjustment for multiple comparisons using the Hochberg modification to the Bonferroni adjustment. The Bonferroni adjustment is a simple function of the raw p-values and is computationally

quick but can be too conservative. Step-down methods remove some conservativeness, as do the step-up methods described by Hochberg (1988). The modification procedure rejects all hypotheses with smaller or equal p-values to that of any one found less than its critical value, defined as $(i/m)/Q$ (where I = the individual p-value rank; m = the number of tests; and Q = the false discovery rate). Essentially, if the largest p-value for these two comparisons is < 0.05 , then both tests are considered statistically significant. However, if the largest p-value is > 0.05 then the next largest p-value will be assessed for statistical significance (adjusting for multiple comparison) relative to the number of tests being performed (i.e.: $0.05/2 = 0.025$).

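### The PROMIS powers are single-test figures at an unadjusted 0.05; under the planned Hochberg rule, pain-interference power at the final size is about 78–81% (81–84% with no design effect), against the stated 85%

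*SAP*

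**What the plan says.** **Power.** SAP section 6 states that with 608 randomized "the power for the PROMIS Pain Interference score is 96%, while the power for the PROMIS Physical Functioning scale is 57" per cent, assuming 20% missing PROMIS responses. Protocol Table 8 ("Power for Primary and Key Secondary Outcomes with N=608 Randomized Participants") has the same two figures, and the protocol text (section 5.4) ties them to a 25% allowance. For the final 526, Table 6.1 gives "85% Based on number of completed surveys" for pain interference and "40% Based on number of completed surveys" for physical function. The inputs are the same throughout: "the MID for the pain interference scale is 3.5 units", the MID for physical function is 2, and the SD of change is 10 for both. SAP section 6 names a significance level of 0.05 for the MED calculation, but its text gives none for the PROMIS powers and does not mention multiplicity. Protocol section 5.4 wants at least 80% power for pain interference.

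**Testing.** SAP 7.6 assesses the two outcomes "using the Hochberg modification to the Bonferroni adjustment (discussed further in section 9.5.1"), and protocol section 5.1 says the same. SAP 9.5.1 explains the rule. If the larger p-value is below 0.05, both outcomes are significant; otherwise the smaller must meet 0.05/2 = 0.025. Just before that, the same section prints the critical value as (i/m)/Q ("where I = the individual p-value rank; m = the number of tests; and Q = the false discovery rate").

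**The concern.** Under Hochberg, pain interference gets the 0.05 level only when physical function is also below 0.05. Physical function has a stated power of only 40%, so in most replications pain interference must clear 0.025. A power computed at a flat 0.05 is then too high for the planned analysis.

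Non-significant results are to be read as inconclusive, and the stated power tells a reader how informative such a result is. The printed 85% clears the protocol's 80% target by five points. The question is whether the planned procedure does so too.

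The threshold formula in SAP 9.5.1 is a second, smaller fault in the section that defines the multiplicity procedure.

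**Working it through.** **Inputs.** Differences 3.5 and 2, SD 10, 526 randomized, survey completion around 60% (all SAP section 6); 1:1 allocation (SAP 4.3); two-sided tests (SAP 7.1). Group size 8 and intraclass correlation 0.01 (SAP section 6) give a design effect of 1 + (8 − 1) × 0.01 = 1.07. Assumed, because the documents do not give it: a correlation of 0 to 0.7 between the two outcomes, both scored towards benefit.

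**Formula.** For total N, SE = 10 × √(4/N) and power = Φ(difference/SE − z), with z = 1.960 at 0.05 and z = 2.241 at 0.025.

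**Step 1: reproduce the stated figures at 0.05.**
- Final: 526 × 0.60 / 1.07 = 295, SE = 1.1645. Pain interference: 3.5/1.1645 = 3.006, Φ(3.006 − 1.960) = 85.2%. Physical function: 2/1.1645 = 1.717, Φ(1.717 − 1.960) = 40.4%. Stated: 85% and 40%.
- Planned: 608 × 0.75 = 456 gives 96.2% and 57.0%; 608 × 0.80/1.07 = 455 gives 96.2% and 56.8%. Stated: 96% and 57%.
- Without a design effect, 526 × 0.60 = 316 gives 87.5% and 42.7%, a poorer match.
- The protocol's sizes for 80% power (260 and 786) come out as 258 and 786 at 0.05. At 0.025 they would be 312 and 952.

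**Step 2: the same sizes at 0.025.**
- N = 295: 77.8% and 30.0%
- N = 316: 80.7% and 32.1%
- N = 456: 93.3% and 45.8%

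**Step 3: the Hochberg rule.** At zero correlation the power for one outcome is

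P(p < 0.025) + P(0.025 ≤ p < 0.05) × P(other p < 0.05).

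Pain interference at N = 295:
- Physical function at its MID: 0.778 + (0.852 − 0.778) × 0.404 = 0.808
- Physical function with no effect: 0.778 + 0.074 × 0.05 = 0.781

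Simulating the two-test rule over correlations 0 to 0.7 gives:

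| N | Pain interference, single test at 0.05 | Hochberg, physical function at MID | Hochberg, physical function no effect |
|---|---|---|---|
| 295 | 85.2% | 78.6–80.8% | 78.0–78.2% |
| 316 | 87.5% | 81.4–83.6% | 81.0–81.1% |
| 456 | 96.2% | 93.5–94.9% | 93.4–93.6% |

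| N | Physical function, single test at 0.05 | Hochberg, pain interference at MID | Hochberg, pain interference no effect |
|---|---|---|---|
| 295 | 40.4% | 38.9–40.0% | 30.1–30.5% |
| 316 | 42.7% | 41.4–42.4% | 32.1–32.6% |

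**Step 4: the printed formula.** With m = 2 and Q = 0.05, (i/m)/Q gives (1/2)/0.05 = 10 and (2/2)/0.05 = 20, so every p-value would pass. Hochberg's critical value is alpha/(m − i + 1), with i counted from the smallest p-value: 0.05/2 = 0.025 and 0.05/1 = 0.05, which is the rule SAP 9.5.1 then states. Multiplying by Q instead of dividing gives the Benjamini-Hochberg form. For two tests its thresholds are also 0.025 and 0.05, but it is a different procedure and controls a different error rate.

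**The case against.** **The 85% is not a miscalculation.** It is correct as the power of one test at 0.05, and the row is headed as approximate. The Table 6.1 column headings carry note markers whose text is not in the copy read here, so a note may state the basis. What stands is that neither the SAP section 6 text nor the visible note to protocol Table 8 gives it.

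**The size of 295 is back-solved.** SAP section 6 describes the design effect only for MED, and it states the PROMIS basis as completed surveys, about 316. Protocol Table 7 does include within-cohort correlation in the PROMIS allowances, but no document gives a PROMIS design effect. At 316 the Hochberg power is 81–84%, only one to four points below the stated 85%. That is why both sizes are shown. Like for like the gap persists: 316 gives 87.5% unadjusted.

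**The gap lies within input uncertainty.** If the SD were 9.5, Hochberg power at 295 would be 83–85% with physical function at its MID. That is true, but the single-test figure would also rise, to 88.6%.

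**The formula misleads nobody in practice.** The sentences after it give the right thresholds. It remains an error in operative text. A reader might infer that the plan controls a false discovery rate, or that the decision rule is unsound; the Hochberg procedure named in SAP 7.6 and 9.5.1 and in protocol section 5.1, and the 0.05 and 0.025 stated in 9.5.1, do not support that.

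**The primary column.** Because SAP section 6 reports "As of June 2023 (DSMB report), study discontinuation was at 20" per cent, a reader might infer that the 75% for MED should use 20% missing rather than 12%. The documents do not support this. The cell states that it uses the protocol-assumed level. SAP 4.6 plans to keep extracting EHR data after discontinuation, apart from certain withdrawal categories. Protocol section 5.3.3 expects dose data to be nearly complete. Study discontinuation is not the missing-prescription rate, and no such rate is given.

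**Conclusion.** The point holds for pain interference. The PROMIS powers in SAP Table 6.1 and protocol Table 8 are those of single tests at 0.05, not of the planned Hochberg procedure. Comparing each size with its own single-test figure, the loss at the final size is about four to seven points, and the corrected 78–84% no longer clearly exceeds the 80% target. In the planned row, at 608 with 25% missing, the loss is one to three points.

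A reader might infer that physical-function power also falls materially. It does not when pain interference is at its MID: it stays at about 39–43%, the upper end being the unadjusted value at 316. The figure of about 30–33% belongs to the different scenario in which pain interference has no effect.

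The sizes rest on the stated SD of 10, the approximate 60% completion, the choice of design effect, and a non-negative correlation of up to 0.7. Enrolment is closed, so this concerns how the results are read; it changes no design decision, test or estimate.

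**What to change.** 1. In SAP section 6 and Table 6.1, and in protocol section 5.4 and Table 8, restate the PROMIS powers under the Hochberg rule, with the number of completers, design effect and correlation assumed. At minimum, label the present figures as unadjusted two-sided 0.05 and put the 0.025-level figures beside them: 77.8% and 30.0% at 295, or 80.7% and 32.1% at 316, for the final row; 93.3% and 45.8% at 456 for the planned row.
2. In SAP 9.5.1, replace (i/m)/Q with alpha/(m − i + 1), i ranked from the smallest p-value, and remove the reference to a false discovery rate. The 0.05 and 0.025 rule already there stays as it is.
3. Leave the primary MED column unchanged.

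The cost is a few table cells with matching text in both documents, one formula, and a slightly less favourable stated power for pain interference.
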